In this study, the mitoPO2 of the skin will be measured. Reliable measurements can only take place with sufficient concentrations of protoporphyrin IX in the mitochondria. Therefore, a self-adhesive patch containing 8mg of ALA (Alacare®; Spirig AG, Egerkingen, Switzerland) will be placed on the anterior chest wall for induction of PpIX, for at least 4 hours before the first measurement can take place. To enhance ALA penetration, the skin will be rubbed with alcohol to remove the exposed layers of stratum corneum. Hair, if present, will be shaved. Following at least 4 hours induction of PpIX, the ALA patch will be removed after the outline of the ALA patch is marked. To create steady and reliable

measurements, a specially designed plaster will be used to attach the COMET Skin Sensor (COMET Skin Sensor, Photonics Healthcare, the Netherland) to the skin. This plaster is referred to as the Skin Pad, it is not CE marked, and is adhesive on both sides. One side of the plaster is a silicon skin friendly side and the other a strong acrylic adhesive to which the Skin Sensor is attached.

Figure 2: Skin Pad

After placing the skin sensor, calibration measurements will be made to ensure the quality of the measurements. Thereto, 5 measurements will be made in the first minute to establish a reliable and stable measurement. Occlusion of the microcirculation will be accomplished via local pressure with the measurement probe, which we use to validate the actual mitoPO2 measurement. After these measurements, mitoPO2 will be measured each minute for 5 minutes to obtain a mean mitoPO2. To ensure that no other variables influence the measurements, measurement characteristics will be logged. In this log, the circumstances in which each measurement is made will be documented. Known intervening variables include, for example, skin temperature, thus skin temperature will be recorded. Other variables recorded in the log will be vasopressor use, dosage of the vasopressor, and nurse actions. Following mitoPO2 measurement, the ALA patch will be re-used to protect the exposed skin for phototoxicity until the next measurement. After completion of the mitoPO2 measurements the exposed skin will be protected from sunlight for 24 hours. An overview of the mitoPO2 measurement is given below.

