### **5.1.2 Clinical Care**

It is standard clinical practice that most patients receive a central venous (vena jugularis, incidentally vena subclavia) and an arterial (arteria radialis) catheter when admitted to the intensive care unit. Patients with anaemia having an arterial catheter will be included in the study. During the pilot phase of the study, patients did not need to have a central venous catheter since the pilot study is about the feasibility of the mitoPO2 measurement and not the outcomes. Blood samples will be drawn from these catheters. Patient management will take place according to usual care. When patients meet the inclusion criteria, an ALA-patch will be placed. After at least four hours PpIX induction, the cutaneous mitoPO2 sensor will be placed to make the first measurements. Transfusion will be given in an one hour. The clinician can deviate from this time frame if the condition of the patient doesn't permit a 1 hour lead time. After red blood cell transfusion, measurements of the mitoPO2 will be made at predefined moments.

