### 5.3.4 Sample handling and Measurements:

Samples will be collected from

- central venous catheter (if applicable)
- arterial catheter

In order to make comparisons between different compartments of the body, blood samples (arterial, central venous) and cutaneous samples will be collected at predefined moments.

These moments during the pilot study are:

- Before transfusion (=T0)
- At the end of each transfusion (=T1)
- 30 minutes after T1 (=T2)
- 60 minutes after T1 (=T3)
- 180 minutes after T1 (=T4)
- 24 hours after T1 (=T5)

With the help of the pilot study, an overview of the measurements and parameters were made.

With the help of this overview, decisions were made regarding the number of measurement moments (e.g. no need for measurement 15 minutes after red cell transfusion). Details about which parameters are determined at each time point during this pilot study are described in appendix 2. For the laboratorial measurements a total of 42ml of blood will be taken (10ml at T0 and T5, 4ml at T1 and T2, 6ml at T3 and 7.5ml at T4). As can be seen in appendix 2, most of the measurements are part of standard care which minimalizes the burden for the patient.

Figure3: Measurement MitoPO2 with the Comet

Analysis of red blood cell transfusion on the intensive care unit at LUMC showed 69% of transfusions occurred during daytime (between 8.00hr and 18hr). The remaining transfusions were evenly distributed in the evening and night time. Since transfusions outside the normal daytime are mostly because of urgent medical reasons, no measurements will be done in the evening or night.

Besides time of transfusion, analysis of previous ICU data showed that the mean duration elapsing between the decision of a non-emergency red cell transfusion and the start of the transfusion is 2-3 hours. Thus, maximum of 2 hours delay for start of transfusion during this study is achieved. However, at no time red cell transfusion will be delayed if the patient is clinically in need of a transfusion in order to have enough time to induce PpIX. To ensure this, the clinician responsible for the patient, and not the researcher, has the final decision in the timing of the red cell transfusion. The delay of transfusion will be recorded to gain an insight in delay of transfusion.

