3. ALA patch and sensor fixation: The dermatologic agent 5-aminolevulinic acid (ALA) is applied to the patient skin. The sensor is fixated to the site with the help of a patch on which the skin sensor is placed. Simple ALA patches were developed by Photonamic and are marketed for photodynamic therapy, ALA crèmes are available from Galderma, photocure, DUSA and Biofrontera. This set up allows the physician to place the ALA-patch anywhere on the patient's skin and, after four hours, place the sensor to locally determine the mitoPO2 level in the cells of the epidermis, which is then displayed on the monitor. Measurements can be performed every second for several minutes, or every few minutes for a period of 24 hours on the same spot of skin. After that, another location for the patch should be chosen.

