
Standard measurements
	
 
•Daily                     
 
•creatinin, Hb, Ht, lactate, SaO2, ScvO2, PvO2, PvCO2, PaO2, PaCO2
 
•ECG
 
•APACHE II and IV (at admission), SOFA, RIFLE
 
 
 
•Continu                     
 
•SpO2, HF, BP, CVD, UP, ICDSC, RASS, GCS
 
•inotropic therapy, vasopressor use
 
•fraction of inspired oxygen, mechanical ventilation duration and setting, renal replacement duration and settings
 
 
 

Extra determinations
	
 
•troponin
 
•CK
 

Extra measurements
	
 
•mitoPO2 at T0-T5
 
•ScvO2, SaO2, PaO2, PaCO2, PvCO2, PvO2 and lactate at T1-4
 
•Hb measurement at T3
 
•Cardiac index measurement with Vigileo II at T0 and T5
 
•Microcirculation with sublingual SDF imaging at T0 and T5
 

**Abbreviations:** BP= blood pressure; CK= creatinine kinase; CI= cardiac index; CVP= central venous pressure; ECG= electrocardiogram; FB= fluid balance; FiO2= fraction inspired oxygen; GCS= Glasgow coma scale; Hb= haemoglobin; HF= heart frequency; Ht= haematocrit; ICDSC= intensive care delirium screening checklist; ICU= intensive care unit; NYHA= New York Heart Association class; PaO2= arterial oxygen tension; PvO2= venous oxygen tension; RASS= Richmond agitation- sedation scale; RIFLE= Risk, Injury, Failure, Loss of kidney function, and End-stage kidney disease classification ; SaO2= arterial saturation; ScvO2= central venous oxygen saturation; SDF= side stream dark field imaging; SOFA= sequential organ failure assessment; SpO2= peripheral oxygen saturation; UP= urine production.

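### Does the mitoPO2 reading 24 hours after transfusion outlast the 24 hours that the device background describes for one spot of skin?

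*Protocol*

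**What the plan says.** **Device background (Protocol, Appendix 1, Background on the measurement).** The sensor goes on four hours after the ALA patch. Readings can then be taken at very short intervals over a brief spell. The longer pattern described is "every few minutes for a period of 24 hours on the same spot of skin. After that, another location for the patch should be chosen".

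**Study schedule (section 5.3.4; Appendix 2).** T0 is before transfusion, T1 at its end, T4 is 180 minutes after T1, and the last reading is "24 hours after T1 (=T5". Appendix 2 lists "mitoPO2 at T0-T5". It also lists "Microcirculation with sublingual SDF imaging at T0 and T5" and "Cardiac index measurement with Vigileo II at T0 and T5".

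**Transfusion time (section 5.1.2).** "Transfusion will be given in an one hour". This is not rigid: "The clinician can deviate from this time frame if the condition of the patient" does not allow it.

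**Site and checks (section 4, Investigational product).** The patch stays on for at least four hours, then "the ALA patch will be removed after the outline of the ALA patch is marked". The same patch covers the skin between readings, and no second patch or site is described. Each measurement has five calibration readings in the first minute, an occlusion check, and then one reading a minute for five minutes. A log records the circumstances. The items named are skin temperature, vasopressor use and dosage, and nurse actions.

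**The concern.** Read side by side, the appendix seems to set a 24-hour limit for one patch site, and the schedule seems to break it for every patient. T5 is counted from the end of transfusion, so no transfusion, however short, brings it within 24 hours of T0.

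Section 4 makes a reliable reading depend on enough protoporphyrin IX in the skin. The specifications in Appendix 1 give the monitor's tolerance only for signal quality above 75%. The log names neither signal quality nor time since the patch was placed. If the signal had faded by T5, the value might be less accurate, and the study file might not show it.

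What would be at stake is the only mitoPO2 value about a day after transfusion. It is also the only post-transfusion value at a time point shared with the sublingual imaging, and the association of mitoPO2 with the microcirculation is a secondary endpoint.

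**Working it through.** **Inputs**
- Induction before the first reading: at least 4 h (section 4).
- Transfusion time d: 1 h planned (section 5.1.2). A value of 0.5 h is used as an assumed shorter case, and 2 h and 3 h as assumed longer ones.
- T4 = T1 + 3 h and T5 = T1 + 24 h (section 5.3.4).
- Period on one spot: 24 h (Appendix 1).
- T0 is taken immediately before the transfusion starts. An earlier T0 lengthens every interval counted from T0 or from patch placement.

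**Formulas**
- T0 to T5 = d + 24
- Patch to T5 = 4 + d + 24
- T0 to T4 = d + 3
- Patch to T4 = 4 + d + 3

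| d | T0 to T5 | Patch to T5 | T0 to T4 | Patch to T4 |
|---|---|---|---|---|
| 0.5 h | 24.5 h | 28.5 h | 3.5 h | 7.5 h |
| 1 h (planned) | 25 h | 29 h | 4 h | 8 h |
| 2 h | 26 h | 30 h | 5 h | 9 h |
| 3 h | 27 h | 31 h | 6 h | 10 h |

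**When the 24 hours start.** Appendix 1 gives the order: patch, four hours, sensor, then a period of readings. On that order the period begins when induction ends and runs to 4 + 24 = 28 h after the patch. With d = 1 h, T5 comes at 29 h, so the overrun is 29 − 28 = 1 h, which is d itself. An overrun of 29 − 24 = 5 h appears only if the period starts at patch placement, and the order of the sentences does not suggest that.

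**What is affected.** One of six time points. T0 to T4 lie inside 24 h on either count. Section 5.4.1 defines the primary endpoint as the change from before to after transfusion and ties it to no single time point. Four post-transfusion readings (T1 to T4) are untouched.

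**What shares T5.** Appendix 2 lists cardiac index at T0 and T5, but section 5.3.5 has cardiac output measured continuously. T5 is therefore not the only occasion on which the two can be compared. The argument that T5 is the sole shared post-transfusion point holds for the sublingual imaging only.

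**What the record holds.** The log in section 4 is meant to document the circumstances of each reading. Its items are introduced as examples there and again in section 5.3.1, so the list is open. Section 9.1 says that the device stores the date and time of measurement and that its data are downloaded. Time since the patch follows from that if the time of placement was charted. Whether the download carries signal quality is not stated.

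**The case for a change.** The strongest case for acting is that the remedy is almost free while the loss could be permanent. One sentence would settle how the 24 hours apply, and two more fields in an existing log would let every T5 value be checked against the device's own threshold. Section 9.1 says the device can retrieve only the current or most recent series. If signal quality is neither written down nor exported, no later analysis can recover it. Moving the small sensor area within the patch outline does not remove the mismatch either, because Appendix 1 speaks of another location for the patch itself.

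Part of this stands. The passages do not match to the hour, one site is described for all readings, and nothing states whether the 24 hours cover short intermittent series.

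The rest does not carry the weight. The appendix says what the device can do when read every few minutes; it does not govern a sixth short series. The limit to the most recent series is met by the planned download. Exact log fields are case-report-form detail, and the point about signal quality applies equally to T0 to T4, so it does not arise from the 24-hour sentence. The schedule was also reviewed after the pilot. The summary of changes for version 3.0 records that two moments, 15 and 120 minutes, were dropped for reasons that included stability of the measurement, and the 24-hour reading was kept. That does not prove T5 valid, since no T5 quality data are given, but it was not left unexamined.

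**Conclusion.** No change follows. The mismatch is genuine and small: T5 is about 25 hours after T0 against a nominal 24, an overrun equal to the transfusion time, at one of six time points. This assumes a one-hour transfusion, T0 just before its start, and a 24-hour period that begins after induction. Longer transfusions widen the overrun hour for hour.

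Nothing in the document shows that accuracy falls at that point. The size of any error cannot be derived from it, and the primary endpoint is not shown to be affected. A clarifying sentence would record how a background description applies. Two named log fields would spell out what an open list already permits. Neither would set a rule that changes an estimate or a conclusion. An analyst who doubts T5 can use the calibration and occlusion results, the time stamps and the log, and can compare results with and without it.

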#### The measurement specifications:

Photonics Healthcare's COMET monitor measures absolute oxygen availability precisely and exactly where it is needed: in the mitochondria of the active cells. This provides doctors with quantitative insight in the availability and consumption of oxygen in their patients' cells and hence the need for a blood transfusion. To determine the oxygen tension in the mitochondria, the COMET measures the

lifetime of the triplet state of protoporphyrin IX (PpIX), a precursor of haeme and hence haemoglobin. The discovery that PpIX exhibits a 'glow-in-the-dark' effect with an oxygen-dependent life time was published in a Nature journal; patents are awarded in Europe and the US and exclusively licensed by PH. The COMET probes the tissue with very short pulses of green light generated by a diode-pumped solid state laser. This light is brought to the site via an optical fibre. The COMET then observes the decay of the intensity of delayed fluorescence from the red spectrum of light collected from the tissue in the first milliseconds after the flash. Under normal conditions, PpIX is present in very low concentrations due to the presence of a negative feedback loop in which a product of PpIX, haeme, acts to inhibit the production of aminolevulinic acid (ALA), a substrate for PpIX. This can be overcome by the exogenous administration of ALA, which on its turn leads to higher concentrations of protoporphyrin IX in the mitochondria. ALA patches are already used in and approved for the therapy of benign skin disorders with Photodynamic Therapy (PDT). Its use is safe and provides good treatment results with excellent cosmetic outcome. The 2x2cm large Alacare patches (8mg) were developed by Photonamic and are marketed for the treatment of actinic keratosis, a benign skin disorder, with photodynamic therapy.

The key specifications of the COMET sensor system are:

- Detection range: 0 – 200 mmHg (arterial oxygen tension does not exceed 100 mmHg in normal physiologic situations).
- Tolerance of Monitor: +/- 15%, at least +/- 3 mmHg, for signal quality >75%, which is similar or better than many clinical measurement systems such as cardiac output (+/- 30%), tissue oxygen (+/- 30%) or haemoglobin (+/-20%). Repeatability and stability of the measurement is high and absolute accuracy will improve as more information about the new measurement becomes known but already is higher than for some current parameters used in the clinic (for example cardiac output).
- Time to result: 1 second (for a prepared measurement location, i.e. placement of ALA-patch 4 hours previously to measurement).
- Simple handling (one hour of training is sufficient to train any doctoral student, nurse or doctor)
- All-in-one system, no need for other equipment or control mechanisms.

#### **Current stage of development:**

The COMET measurement system has been developed based upon applicable regulations, standards (Medical device directive 93/42EEC, IEC 60601 rev 3, ISO 13485) and has been tested in preclinical tests and volunteer studies. The key milestones are described below.

The crucial step in the invention is the exploitation of the oxygen dependent optical properties of protoporphyrin IX. Because this substance is made in the mitochondria and can be measured on the skin, the problem of signal location that has made all earlier attempts to directly measure cellular metabolism unsuccessful is solved. First publication of the feasibility of the measurements was in 2006 in Nature Methods.

Subsequently the methods was tested in vivo on various organs, validated against existing technologies and showed the measurement could be used to measure oxygen consumption i.e., cellular energy turnover in a first human volunteer. Further studies demonstrated that cellular oxygen availability and consumption can safely be measured using ALA patches and COMET prototypes in a study in 30 human volunteers at Erasmus MC in Rotterdam. it was shown that information from the skin is representative for other parts of the body. From September 2014 until April 2015, Van Diemen et al. measured the increase of cellular oxygen consumption with the COMET prototype in skin of 28 human volunteers after 4 weeks of daily statin use (Simvastatin, a cholesterol lowering drug suspected of modifying mitochondrial function) and its partial reversal by additional intake of ubiquinol (Q10), which contributes to mitochondrial function. Next to the COMET the study also measured phosphocreatine recovery time after muscle exercise in 7-Tesla-31P-MR spectroscopy and mitochondrial membrane potential in white blood cells. The practically perfect correlation of the results in all groups is a strong validation of PH's measurement against a very expensive and cumbersome technique.

PH developed the COMET monitor, the first clinical monitor for cellular oxygen and conducted preclinical research with the help of partners, a Eurostars grant and investors.

In patients receiving ALA assisted photodynamic therapy and during neurosurgery oxygen levels were measured with the COMET. These demonstrate that the COMET can be used in patients and measurements are stable. The study in this project will take the first step towards the use of this technology for blood transfusion in critically ill patients.


Standard measurements
	
 
•Daily                     
 
•creatinin, Hb, Ht, lactate, SaO2, ScvO2, PvO2, PvCO2, PaO2, PaCO2
 
•ECG
 
•APACHE II and IV (at admission), SOFA, RIFLE
 
 
 
•Continu                     
 
•SpO2, HF, BP, CVD, UP, ICDSC, RASS, GCS
 
•inotropic therapy, vasopressor use
 
•fraction of inspired oxygen, mechanical ventilation duration and setting, renal replacement duration and settings
 
 
 

Extra determinations
	
 
•troponin
 
•CK
 

Extra measurements
	
 
•mitoPO2 at T0-T5
 
•ScvO2, SaO2, PaO2, PaCO2, PvCO2, PvO2 and lactate at T1-4
 
•Hb measurement at T3
 
•Cardiac index measurement with Vigileo II at T0 and T5
 
•Microcirculation with sublingual SDF imaging at T0 and T5
 

**Abbreviations:** BP= blood pressure; CK= creatinine kinase; CI= cardiac index; CVP= central venous pressure; ECG= electrocardiogram; FB= fluid balance; FiO2= fraction inspired oxygen; GCS= Glasgow coma scale; Hb= haemoglobin; HF= heart frequency; Ht= haematocrit; ICDSC= intensive care delirium screening checklist; ICU= intensive care unit; NYHA= New York Heart Association class; PaO2= arterial oxygen tension; PvO2= venous oxygen tension; RASS= Richmond agitation- sedation scale; RIFLE= Risk, Injury, Failure, Loss of kidney function, and End-stage kidney disease classification ; SaO2= arterial saturation; ScvO2= central venous oxygen saturation; SDF= side stream dark field imaging; SOFA= sequential organ failure assessment; SpO2= peripheral oxygen saturation; UP= urine production.

## 15. Appendix 3: Skin Pad

### 1. Description

The Skin Pad is a non-sterile, single use device to forcefully hold a sensor in optical access on intact skin for no more than 24 hours.

The fixation of a sensor with the Skin Pad is designed to provide a steady and reliable measurement and allow repeated or continuous measurements over longer time periods that do not require the user to hold the sensor or fix it with tape that might cause changes to the signal.

The Skin Pad on the skin with a sensor attached is shown in Figure 1.

The Skin Pad consists of three layers and a release liner on each side to protect the adhesive surfaces before use.

The central layer is a thin polyurethane film, double coated with a silicone gel adhesive and acrylic adhesive on the opposite side (Scapa Soft Pro 6051). The silicon adhesive layer covering the entire surface area of the “skin side” of the Skin Pad is covered with a yellow LDPE release liner (Figure 2). Once this release liner is removed the silicon adhesive makes it possible to attach the sensor on the desired location on intact skin and reposition it several times. The adhesive power of the silicon adhesive is designed for sensitive skin and is called “skinfriendly”.

The “sensor side” of the Skin Pad is covered with a white PE foam (Scapa 9868/824) except for a central part with the dimensions of the sensor where the acrylic adhesive is exposed and where the sensor should be attached. The exposed acrylic adhesive is covered with a white release liner with a lip for easy removal before the skin sensor is attached.

Small notches on the side of the Skin Pad can assist in orientation. For a sensor with an active measurement area 14 mm from the end of the sensor, these notches indicate the location of the measurement area in the midline of a sensor attached inside the clear adhesive area surrounded by the white foam. The Skin Pad should then be attached to the skin so that the mid-line of the Skin Pad and the line connecting the notches intersect at the center of the desired measurement location.

Between the film and the foam, not accessible to the user or patient, is a metalized white polypropylene film fixed to the film with a medical-grade rubber adhesive (Bioflex Rx848P). This layer will largely block ambient light to reduce the noise for the measurements.

[figure not shown]

Figure 1: Skin Pad on the arm fixing a sensor next to a measurement device

Figure 2: Yellow release liner of Skin Pad

Figure 3: Top view of sensor with white release liner

